4.3 Primary Analysis

After the last enrolled and randomized subject in Stage 2 has completed all Week 12 assessments or been lost to follow-up, all outstanding data queries related to primary analysis have been resolved or determined to be unresolvable, and the data have been cleaned, finalized and locked, the study blind will be broken, and the primary analysis of the efficacy and safety data will be performed. The primary analysis at Week 12 will include all population analyses and endpoints using pooled data from all subjects enrolled and randomized in Stage 1 and 2 (**Table 4: Summary of Primary and Secondary Efficacy Endpoints at Week 12**).

Table 4: Summary of Primary and Secondary Efficacy Endpoints at Week 12

Endpoint	Display	ITT	PTE	Sensitivity	Subgroup	Missing Data Imputation
Primary						
ACR20 response	T, L	Y	Y	Y [1]	Y	NRI
Key Secondary Adjusted for Multiplicity						
ACR20 response from Day 0	T, L	Y	Y	Y [1]	Y	NRI
DAS28-CRP good/moderate EULAR response	T, L	Y	Y	Y [2]	Y	NRI
DAS28-CRP response (MCID)	T, L	Y	Y	Y [2]	Y	NRI
HAQ-DI response (MCID)	T, L	Y	Y	Y [2]	Y	NRI
Exploratory Secondary [3]						
ACR50/70 response	T, L	Y	--	--	--	--
ACR Components (TJC28, SJC28, Subject Pain, SGA, EGA, HAQ-DI, hsCRP) 20/50/70 response	T, L	Y	--	--	--	--
Mean HAQ-DI score change at Week 12	T, L	Y	--	--	--	--
DAS28-CRP score change, LDA/remission	T, L	Y	--	--	--	--
CDAI score change, LDA/remission, response	T, L	Y	--	--	--	--
SF-36/PCS/MCS score change	T, L	Y	--	--	--	--
EQ-5D-5L score change	T, L	Y	--	--	--	--
RAMRIS (bone erosion, osteitis, synovitis, CARLOS) score change, progression (bone erosion)	T, L	Y	--	--	--	--
Percent change in plasma biomarkers	T, L	Y	--	--	--	--
BI for subject's blinding assessment	T, L	Y	Y	--	--	--
BI for Joint Evaluator's blinding assessment	T, L	Y	Y	--	--	--
BI for Co-PI Rheumatologist's blinding assessment	T, L	Y	Y	--	--	--

Abbreviations: ACR, American College of Rheumatology; BI, Bang's blinding index; CARLOS, cartilage loss score; CDAI, Clinical Disease Activity Index; CRP, C-reactive protein; DAS, Disease Activity Score; EGA, evaluator's global assessment; EQ-5D-5L, EuroQol 5 domains 5 levels; EULAR, European League Against Rheumatism; HAQ-DI, Health Assessment Questionnaire Disability Index; hsCRP, high sensitivity CRP; ITT, intent to treat; L, listings; LDA, low disease activity; NRI, non-responder imputation; PTE, per treatment evaluable; RAMRIS, Rheumatoid Arthritis MRI Scoring System; SF-36, Short Form Survey with 36 items; SGA, subject's global assessment; T, tables; TJC, tender joint count; SJC, swollen joint count; Y, yes.

Note: All response rates are at Week 12 based on change from baseline, unless stated otherwise. Refer to Section 8.1 for definitions of missing data imputation strategies. Refer to Sections 8.2, 8.3, 8.4 and 8.6 for definition of response for specific endpoints. All score values are determined at all timepoints and for change from baseline.

[1] Sensitivity analyses for rescue treatments and missing data.

[2] Sensitivity analysis for timing of baseline, rescue treatments and missing data.

[3] Approaches to handling of missing data are given in Section 8.1

5 STATISTICAL METHODS

5.1 General Considerations for Data Analyses

The primary efficacy endpoint, all secondary efficacy endpoints, exploratory analyses identified here, and safety evaluations are considered *a priori* analyses because they have been prespecified in the SAP prior to locking the dataset and reviewing unblinded results. All other analyses, if any, designed subsequent to locking the dataset will be considered *post-hoc* analyses, and their results will be considered exploratory. Any *post hoc* analyses will be clearly identified in the clinical study report.

Continuous data will be summarized in terms of the mean, SD, median, minimum, maximum and number of observations, unless otherwise stated. The minimum and maximum will be reported to the same number of decimal places as the raw data recorded in the database. The mean and median will be reported to 1 more decimal place than the raw data recorded in the database. The SD will be reported to 2 more decimal places than the raw data recorded in the database. In general, the maximum number of decimal places reported shall be 4 for any summary statistic.

Categorical data will be summarized in terms of the number of subjects providing data at the relevant time point, frequency counts and percentages. If not stated otherwise, percentages will be presented with one decimal place. Percentages will not be presented for zero counts. Percentages will be calculated using n as the denominator. 100% will be presented without decimal places.

P-values greater than or equal to 0.001, in general, will be presented to 3 decimal places. P-values less than 0.001 will be presented as “< 0.001”.

95% Confidence intervals (CI) will be presented to 1 more decimal place than the raw data. Unless stated otherwise, a two-sided 95% confidence level will be calculated when confidence interval is presented.

Data from the protocol-specified visits (i.e., as reported in CRF) will be used in the summary tables (**Appendix B**) and data listings (**Appendix C**). All report outputs will be produced using a software package widely recognized as acceptable for analyzing clinical data in a secure and validated environment.

The analyses for the primary and secondary efficacy endpoints are detailed below:

- The primary ACR20 response at Week 12 will be analyzed with the Cochran-Mantel-Haenszel (CMH) test. For Stage 1 subjects, stratification factors are prior inadequate response or loss of response to JAKi and RA disease severity of < 4 TJC28 or < 4 SJC28 at Day 0. For Stage 2 subjects, stratification factors are RA disease severity at Day 0 and inadequate response or loss of response to ≥ 4 biological DMARDs with ≥ 2 mechanisms of action. Other binary response endpoints at Week 12 will be analyzed similarly.
- The secondary efficacy endpoints that are continuous variables (change from baseline) will be analyzed using Mixed-effect Model Repeated Measure (MMRM) statistics. The repeated-measures analysis will be based on the restricted maximum likelihood method assuming an unstructured covariance structure to model the within-subject errors. The model, including:

treatment group; stratification factors - inadequate response or loss of response to JAKi and RA disease severity at Day 0 (Stage 1 subjects); RA disease severity at Day 0 and inadequate response or loss of response to ≥ 4 biological DMARDs with ≥ 2 mechanisms of action (Stage 2 subjects); visit (all visits from Week 4 to Week 12); and treatment-by-visit interaction as fixed effects and baseline as a covariate, will be used to test the difference between the treatment and control group in a given efficacy endpoint change from baseline to Week 12. The data collected after receiving rescue therapy will be set to missing. Therefore, the MMRM analysis assumes a missing-at-random (MAR) mechanism for missing data due to dropout and post-rescue data.

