11.5 Day 0 Assessments, Randomization, and Initiation of Stimulation

11.5.1 Day 0 assessments

Subjects approved to initiate study treatment will undergo the following assessments within 14-21 days after Implant Procedure and before randomization:

- Collection of vital signs
- Pregnancy test for female subjects of childbearing potential and confirmation of birth control method (see Section **12.1**)
- RA disease activity assessments (see Section **12.2**)
- SF-36 and EQ-5D-5L questionnaires

- Blood collection for CBC and inflammatory biomarkers (see Section **12.3**)
- Reporting of any AEs, device deficiencies and change in concomitant medications.

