11.5.2 Randomization

Upon completion of all Day 0 assessments, subjects will be randomly assigned in a 1:1 ratio to either treatment or control group using an interactive response technology (IRT) system. Subjects assigned to the treatment group will receive active stimulation for 1 min once per day, and those assigned to the control group will receive sham (non-active) stimulation for 1 min once per day. Subjects and study staff will be kept blinded (see Section **18.3**).

For subjects assigned to the control group, their MicroRegulator will be registered to a prescription rule to deliver a sham stimulation, regardless of the setting assigned. The registration is performed by unblinded technicians at SetPoint Medical who have exclusive access to the subject's treatment assignment. The prescription rule is written in the SetPoint Medical cloud and is received by the site's Prescription Pad when connected to Wi-Fi and then applied to MicroRegulator via Energizer. The prescription rule is not visible to the site personnel to ensure they remain blinded to treatment assignment.

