11.11 Duration of Study Period

The study duration is approximately 84 months (8 months for enrollment into Stage 1, 6 months for a pause in enrollment after Stage 1, 12 months for enrollment into Stage 2, and approximately 58 months for completion of follow-up).

For a given subject, the maximum study duration is 1,899 days (about 5 years, 3 months):

- 30 days from informed consent to Implant Procedure
- 21 days between Implant Procedure and randomization at Day 0
- 84 days (about 3 months) between initiation of stimulation at Day 0 to Week 12

- 1,764 days (about 4 years, 10.5 months) between Week 12 and Week 264

A timeline of the key study visits is provided in **Figure 13**.

[figure not shown]

Figure 13: SPM-020 Study Timeline

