5.3 Baseline

Information and RA disease activity assessments collected during Screening on the day of informed consent will be used to confirm initial eligibility and as the baseline assessments for determination of the primary and key secondary efficacy endpoints (**Table 5**).

Baseline assessments for the exploratory endpoints (e.g., EQ-5D-5L, SF-36, RAMRIS, biomarkers) will be collected during Screening.

Table 5: RA Disease Activity Assessments to Be Collected on the Day of Informed Consent and Used as the Baseline Assessments for Determination of the Primary and Key Secondary Efficacy Endpoints

Endpoint	HAQ-DI	SGA	Subject Pain	TJC28	SJC28	EGA	hsCRP
Primary							
ACR20 response	Y	Y	Y	Y	Y	Y	Y
Key Secondary Adjusted for Multiplicity							
ACR20 response from Day 0	Y	Y	Y	Y	Y	Y	Y
DAS28-CRP good/moderate EULAR response	--	Y	--	Y	Y	--	Y
DAS28-CRP response (MCID)	--	Y	--	Y	Y	--	Y
HAQ-DI response (MCID)	Y	--	--	--	--	--	--

Abbreviations: ACR, American College of Rheumatology; CRP, C-reactive protein; DAS, Disease Activity Score; EGA, evaluator's global assessment; EULAR, European League Against Rheumatism; HAQ-DI, Health Assessment Questionnaire Disability Index; hsCRP, high sensitivity CRP; SGA, subject's global assessment; TJC, tender joint count; SJC, swollen joint count; Y, yes.

Note: All response rates are at Week 12 based on change from baseline at the time of informed consent, unless stated otherwise.

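### The MMRM for the exploratory continuous endpoints omits the continuous Day 0 value measured before randomisation, probably at some cost in precision, and the table shells test Day 0 differences that the model cannot produce

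*SAP*

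**What the plan says.** **Model.** SAP 5.1 analyses continuous change from baseline by MMRM with treatment, stratification factors, visit, and "treatment-by-visit interaction as fixed effects and baseline as a covariate, will be used to test the difference between the treatment and control group". The modelled visits are limited: "visit (all visits from Week 4 to Week 12". The stratification factors include "RA disease severity of < 4 TJC28 or < 4 SJC28 at Day 0", a yes/no factor that enters for both stages.

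**Baseline.** Under SAP 5.3, RA assessments "collected during Screening on the day of informed consent will be used to confirm initial eligibility and as the baseline assessments". For the other measures, "Baseline assessments for the exploratory endpoints (e.g., EQ-5D-5L, SF-36, RAMRIS, biomarkers) will be collected during Screening", so that value need not come from the consent day.

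**Day 0.** Protocol 11.5.1 has subjects who "will undergo the following assessments within 14-21 days after Implant Procedure and before randomization". These include the RA disease activity set, SF-36, EQ-5D-5L and biomarkers. Protocol 11.5.2 then states: "Upon completion of all Day 0 assessments, subjects will be randomly assigned in a 1:1 ratio".

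**Timing.** Protocol 11.11 allows "30 days from informed consent to Implant Procedure" and a further 21 days from implant to Day 0. A footnote to the Protocol section 5.1 flow diagram lets subjects consent before, during or after washout.

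**Shells.** SAP Appendix B, Tables 14.1.2.4 to 14.1.2.12, 14.1.2.14 and 14.1.2.15, show a between-arm confidence interval and p-value for Day 0 change from baseline. The footnotes attribute these to the one-sided MMRM. The biomarker shell, Table 14.1.2.19, has Day 0 summary rows but no Day 0 test.

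**The concern.** Day 0 is the last measurement before allocation. It is closer in time to Week 12 than the consent value, and it follows surgery and any washout. If it predicts Week 12 beyond what baseline and the stratum already explain, leaving it out keeps removable variation in the residual and widens the intervals. Because Day 0 precedes randomisation, adjusting for it does not change the quantity estimated, which remains the arm difference in mean change from baseline to Week 12.

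The shells raise a second problem. A Day 0 arm difference cannot be a treatment effect, so a p-value there has nothing to test. The model in SAP 5.1 has no Day 0 visit and could not supply that p-value. At stake are the precision and readability of the exploratory continuous results: the ACR component scores, DAS28-CRP, HAQ-DI, CDAI, SF-36, EQ-5D-5L and biomarkers.

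**Working it through.** **1. The plan's own figures.** The only power figures concern the binary ACR20 endpoint. At 60% versus 30% with 250 subjects the SAP states 0.959; exact enumeration with the futility stop gives 0.9586. This does not bear on the MMRM. No SD, correlation or power is given for any continuous endpoint, so every correlation below is an assumption.

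**2. Gap from consent to Day 0.** At most 30 + 21 = 51 days.

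**3. Residual variance at Week 12**, as a share of total variance. Let a = correlation of consent with Day 0, b = consent with Week 12, c = Day 0 with Week 12.

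- Consent value only: 1 − b²
- Consent and Day 0: 1 − (b² + c² − 2abc)/(1 − a²)

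Example with a = 0.7, b = 0.5, c = 0.6: the first is 1 − 0.25 = 0.750. The second is 1 − (0.25 + 0.36 − 0.42)/0.51 = 0.627.

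**4. Comparison with the planned model.** The planned model also contains the Day 0 stratum, so a consent-only comparator would overstate the gain. Simulation (2,000,000 normal draws) added a dichotomised Day 0 joint count. The share of subjects below the cut ran from 5% to 50%. The endpoint was either the count itself or a score correlated 0.5 with it.

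| a, b, c (assumed) | Consent only | Planned: consent + stratum | With Day 0 added | Variance cut vs planned | SE cut | N giving the planned precision at 250 |
|---|---|---|---|---|---|---|
| 0.5, 0.5, 0.5 | 0.750 | 0.702–0.745 | 0.667 | 5%–11% | 2.6%–5.5% | 223–237 |
| 0.7, 0.7, 0.7 | 0.510 | 0.470–0.508 | 0.424 | 10%–17% | 5.0%–8.6% | 209–226 |
| 0.7, 0.5, 0.6 | 0.750 | 0.693–0.747 | 0.627 | 9%–16% | 4.8%–8.3% | 210–227 |
| 0.7, 0.4, 0.7 (strong) | 0.840 | 0.676–0.829 | 0.494 | 27%–40% | 14.5%–22.8% | 149–183 |
| 0.7, 0.5, 0.35 (null, c = ab) | 0.750 | 0.750 | 0.750 | 0% | 0% | 250 |

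In the non-null rows the stratum alone recovers about 13% to 57% of the gain when the endpoint is the joint count that defines it. For a score correlated 0.5 with that count it recovers about 3% to 12%.

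**5. Day 0 tests.** The 13 scores are TJC28, SJC28, pain, SGA, EGA, hsCRP, HAQ-DI, DAS28-CRP, CDAI, EQ-5D-5L index, EQ VAS, SF-36 MCS and SF-36 PCS. At one-sided 0.025 the expected number of chance positives is 13 × 0.025 = 0.325. If the tests were independent, the probability of at least one would be 1 − 0.975¹³ = 0.28. The scores are correlated, so 0.28 is only indicative.

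**6. Screening tests.** Table 14.1.2.10 tests the severe HAQ-DI category at Screening, and Table 14.1.2.12 tests CDAI low activity and remission there. Eligibility needs at least 4 tender and 4 swollen joints, so CDAI at consent is at least 4 + 4 = 8. Remission (2.8 or less) is impossible, and that row compares zero with zero.

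**The case against.** The strongest reply is that Day 0 is already used. Randomisation is stratified on Day 0 severity and the MMRM carries that factor. ACR20 from Day 0 is a key secondary endpoint. SAP 8.5.1 repeats the key secondary analyses with Day 0 as baseline, and its shell includes mean HAQ-DI change. This stands in part. A reader might infer that the model ignores Day 0 and leaves chance imbalance wholly uncorrected; the stratum shows otherwise. But a single cut on joint counts says little about SF-36 or a biomarker, and the sensitivity analysis replaces the baseline rather than using both values, for one continuous measure only.

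Day 0 may also be a disturbed measurement. It falls 14 to 21 days after neck surgery, and Protocol 14.2 and 14.3 permit temporary perioperative changes to background therapy, steroids, NSAIDs and opiates. Nor is every consent value taken before washout, since some subjects consent after it, and 51 days is a maximum. These points stand, and they are why the null case belongs in the range.

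The Day 0 p-values can fairly be called a mismatch between shells and text, with an editorial remedy. That is right, but the shells would still put uninterpretable p-values into the report.

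**Conclusion.** The point holds as a likely, unquantified loss of efficiency plus a shell error. The omission of the continuous Day 0 value and the Day 0 tests are plain from the text. The size of the loss is not: about 5% to 17% of residual variance in moderate cases, 27% to 40% in a strong case and none in the null case, all under assumed correlations.

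Three stronger readings are tempting and unsupported:

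- **Precision is lost on every continuous endpoint.** This depends on how Day 0 relates to Week 12 given baseline and stratum, which the documents do not report.
- **The trial's conclusions are at risk.** The primary and all four key secondary endpoints are binary and tested by CMH (SAP 5.1 and 8.5). The affected endpoints are exploratory and outside the Hochberg family. The omission causes no bias and no type I error inflation.
- **All Day 0 measures are tested between arms.** The biomarkers are not.

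The change is still worth making. The data are already collected, and in the null case almost nothing is given up.

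**What to change.** - **SAP 5.1.** Add the Day 0 value of the same measure, with its visit interaction, as a covariate beside baseline for every MMRM endpoint collected at Day 0 (all except RAMRIS). Keep change from the consent or Screening baseline as the outcome.
- **Missing Day 0 value.** State a simple rule so that no subject is dropped, for example imputing the pooled pre-randomisation mean. SAP 5.8.1 covers a missing baseline but not a missing Day 0 covariate, and one missing component makes DAS28-CRP or CDAI missing.
- **Appendix B.** Make the Day 0 and Screening rows descriptive, without between-arm intervals or p-values.

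**Cost.** A short SAP edit, shell deletions and a few degrees of freedom: with three modelled visits, one slope and two interaction terms. No new data are needed. The edit belongs before the primary dataset is locked, because SAP 5.1 classes analyses designed after lock as post hoc.

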5.2 Analysis Populations

Analysis population defines the subjects to be included in an analysis. The primary efficacy analyses for the primary and key secondary endpoints will be conducted on the intent-to-treat (ITT) and per-treatment-evaluable (PTE) populations. The exploratory analyses will be conducted on the ITT population as detailed in **Table 4**. All analysis populations are defined below:

- *ITT population.* All enrolled and randomized subjects in Stage 1 and 2.
- *PTE population.* Subjects from ITT population who have received the assigned treatment, who have no major procedural protocol deviations (see Section 9.2) and for whom follow-up data are available.
- *Safety population.* All enrolled subjects in Stage 1 and 2.

5.3 Baseline

Information and RA disease activity assessments collected during Screening on the day of informed consent will be used to confirm initial eligibility and as the baseline assessments for determination of the primary and key secondary efficacy endpoints (**Table 5**).

Baseline assessments for the exploratory endpoints (e.g., EQ-5D-5L, SF-36, RAMRIS, biomarkers) will be collected during Screening.

Table 5: RA Disease Activity Assessments to Be Collected on the Day of Informed Consent and Used as the Baseline Assessments for Determination of the Primary and Key Secondary Efficacy Endpoints

Endpoint	HAQ-DI	SGA	Subject Pain	TJC28	SJC28	EGA	hsCRP
Primary							
ACR20 response	Y	Y	Y	Y	Y	Y	Y
Key Secondary Adjusted for Multiplicity							
ACR20 response from Day 0	Y	Y	Y	Y	Y	Y	Y
DAS28-CRP good/moderate EULAR response	--	Y	--	Y	Y	--	Y
DAS28-CRP response (MCID)	--	Y	--	Y	Y	--	Y
HAQ-DI response (MCID)	Y	--	--	--	--	--	--

Abbreviations: ACR, American College of Rheumatology; CRP, C-reactive protein; DAS, Disease Activity Score; EGA, evaluator's global assessment; EULAR, European League Against Rheumatism; HAQ-DI, Health Assessment Questionnaire Disability Index; hsCRP, high sensitivity CRP; SGA, subject's global assessment; TJC, tender joint count; SJC, swollen joint count; Y, yes.

Note: All response rates are at Week 12 based on change from baseline at the time of informed consent, unless stated otherwise.

5.4 Study Day Calculation

Study day is calculated relative to the date of Day 0 (randomization) and will appear in the listings where applicable. If the date of event is on or after Day 0, study day will be calculated as:

$$\text{Study day} = \text{date of event} - \text{date of Day 0 (randomization)}$$

5.5 Randomization

After completing the protocol-required assessments at Day 0, all enrolled subjects (i.e., meeting all the inclusion and none of the exclusion criteria in whom the implant procedure was attempted) that were implanted will be assigned in a 1:1 ratio to either the treatment or the control group. The randomization scheme will be generated by the study biostatisticians and implemented centrally through Interactive Response Technology (IRT).

The randomization will be stratified to help ensure balanced distribution between treatment groups. For Stage 1 subjects, stratification factors are inadequate response or loss of response to JAKi and RA disease severity of <4 TJC28 or <4 SJC28 at Day 0. For Stage 2 subjects, stratification factors are RA disease severity at Day 0 and inadequate response or loss of response to ≥ 4 biological DMARDs with ≥ 2 mechanisms of action.

Enrollment will continue until at least 240 and up to 250 subjects are randomized. If there are discrepancies in stratification factor values between the IRT and EDC systems, the data recorded in the EDC will be used for analyses.

5.6 Change from Baseline Calculation

Percent change from baseline to any time point (e.g., Day 0, Week 4, 8 or 12) will be calculated as follows:

$$[\text{Value}_{\text{Post-baseline}} - \text{Value}_{\text{Baseline}}] / \text{Value}_{\text{Baseline}} \times 100$$

A negative value reflects a decrease in a given parameter, while a positive relative difference reflects an increase in the parameter.

5.7 Relative Difference Calculation

Relative difference between treatment and control groups at any time point will be calculated as:

$$[\text{Value}_t - \text{Value}_c] / \text{Value}_c \times 100$$

A negative relative difference reflects a decrease in a given parameter on the treatment side compared to control, while a positive relative difference reflects an increase in the parameter on the treatment side compared to control.

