3.4 Sample Size and Power

The sample size is calculated based on an estimated 60% response rate at Week 12 in the treatment group and 30% response rate at Week 12 in the control group. A sample size of 250 randomized subjects, 125 in each group, offers 96% power to detect a difference of 30% at the one-sided alpha of 0.025. If the true response rates are 50% in the treatment and 30% in the control group, the sample size of 250 subjects has 77% power to detect a difference of 20% at the one-sided alpha of 0.025. The table below provides additional power calculations for 250 subjects using estimated response rates of 20 to 40% in control and 35-70% in treatment (**Table 1**). The table also shows power if enrollment ends at 240 subjects. The decrease in power is <1% for all scenarios and most often <0.5%.

Table 1: Power Calculation Based on Estimated ACR Response Rate

Control (%)	Treatment (%)	Difference (%)	Power N = 250	Power N=240
20	50	30	0.967	0.966
20	45	25	0.917	0.916
20	40	20	0.812	0.807
20	35	15	0.609	0.601
30	60	30	0.959	0.959
30	55	25	0.900	0.898
30	50	20	0.773	0.770
30	45	15	0.555	0.549
40	70	30	0.959	0.958
40	65	25	0.897	0.893
40	60	20	0.762	0.750

All p-values are one-sided based on the chi-square test stratified incomplete response to JAKi and include futility stopping. Power based upon 1,000,000 simulations per scenario.

The smallest statistically significant difference that can be detected in the sample of 250 randomized subjects ranges from 11.2% to 12.8% for control rates of 20% to 40%, respectively.

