8.6.2 Analysis of Exploratory Secondary Endpoints

The following endpoints will be analyzed with the CMH test, as described in Section **5.1**:

- ACR50/70 response at Week 12
- DAS28-CRP LDA/remission at Week 12
- CDAI response at Week 12
- HAQ-DI response at Week 12
- EQ-5D-5L response at Week 12
- RAMRIS bone erosion progression (> 0.5) at Week 12

The MMRM will be used to analyze the following endpoints, as described in Section **5.1**:

- Mean CDAI score change from baseline to Week 12
- Mean HAQ-DI score change from baseline to Week 12
- Mean EQ-5D-5L score change from baseline to Week 12
- Mean SF-36/PCS/MCS score change from baseline to Week 12
- Mean RAMRIS bone erosion, osteitis, synovitis, and CARLOS score change from baseline to Week 12
- Percent change in plasma biomarkers (e.g., IL-6, SAA, MMP3)

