Reference: Listing 16.x.x.x

SOURCE: xxxxx SAS 9.4 {program location} {run date/time}}

Table 14.1.2.18.1
 Co-PI Rheumatologist's Blinding Assessment
 (PTE Population)

Repeat Table 14.2.18 for PTE population

Table 14.1.2.19
 Inflammatory Biomarkers
 (ITT Population)

Variable	Treatment (N=xxx)	Control (N=xxx)
IL-6 (pg/mL)		
Screening (baseline)		
N [1]	xx (xx.x%)	xx (xx.x%)
Mean (SD)	xxx.x (xxx.xx)	xxx.x (xxx.xx)
Median	xxx.xx	xxx.xx
Min-Max	xxx.x – xxx.x	xxx.x – xxx.x
Day 0		
N [1]	xx (xx.x%)	xx (xx.x%)
Mean (SD)	xxx.x (xxx.xx)	xxx.x (xxx.xx)
Median	xxx.xx	xxx.xx
Min-Max	xxx.x – xxx.x	xxx.x – xxx.x
Week 4		
N [1]	xx (xx.x%)	xx (xx.x%)
Mean (SD)	xxx.x (xxx.xx)	xxx.x (xxx.xx)
Median	xxx.xx	xxx.xx
Min-Max	xxx.x – xxx.x	xxx.x – xxx.x
Week 8		
N [1]	xx (xx.x%)	xx (xx.x%)
Mean (SD)	xxx.x (xxx.xx)	xxx.x (xxx.xx)
Median	xxx.xx	xxx.xx
Min-Max	xxx.x – xxx.x	xxx.x – xxx.x
Week 12		
N [1]	xx (xx.x%)	xx (xx.x%)
Mean (SD)	xxx.x (xxx.xx)	xxx.x (xxx.xx)
Median	xxx.xx	xxx.xx
Min-Max	xxx.x – xxx.x	xxx.x – xxx.x
Change from baseline		

CONFIDENTIAL

113 of 158

May not be reproduced outside of SetPoint Medical without written permission from Document Control.

Variable	Treatment (N=xxx)	Control (N=xxx)
N [1]	xx (xx.x%)	xx (xx.x%)
Mean (SD)	xxx.x (xxx.xx)	xxx.x (xxx.xx)
Median	xxx.xx	xxx.xx
Min-Max	xxx.x – xxx.x	xxx.x – xxx.x
Percent change	xx.x%	xx.x%
Relative difference [2]	xx.x%	xx.x%
95% CI for difference [2]	(xx.x%, xx.x%)	(xx.x%, xx.x%)
p-value for difference [2]	0.xxx	0.xxx

Repeat for:

SAA (µg/mL)

MMP-3 (pg/mL)

Abbreviations: IL, interleukin; ITT, intent to treat; MMP, matrix metalloproteinase; SAA, serum amyloid A.

[1] Percentage calculated based on ITT Population.

[2] Relative difference in mean score change from baseline and one-sided p-value based on the Mixed-effect Model Repeated Measure model with PROC MIXED. Stratification factors are inadequate response or loss of response to JAKi and RA disease severity at Day 0 for Stage 1 subjects and RA disease severity at Day 0 and inadequate response or loss of response to ≥ 4 biological DMARDs with ≥ 2 mechanisms of action for Stage 2 subjects.

Reference: Listing 16.x.x.x

SOURCE: xxxxx SAS 9.4 {program location} {run date/time}}

Table 14.1.2.20
 RA Rescue Treatments and Follow-up Interventions
 (ITT Population)

	Treatment (N=xxx)	Control (N=xxx)
Received any post-procedure RA rescue treatment		
Yes [1]	xxx (xx.x%)	xxx (xx.x%)
If yes, first noted at [2]	xxx (xx.x%)	xxx (xx.x%)

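### The biomarker relative difference reverses sign when the control group's mean change is negative, and the SAP does not settle whether percent change or mean change is analysed

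*SAP*

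**What the plan says.** SAP 5.7 introduces the measure with "Relative difference between treatment and control groups at any time point will be calculated as", followed by the control value subtracted from the treatment value, divided by the control value and multiplied by 100. It then gives the reading: "A negative relative difference reflects a decrease in a given parameter on the treatment side compared to control", and the converse for a positive value. No condition is placed on the sign of the control value.

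The only mock-up that prints a relative difference is Table 14.1.2.19 (Inflammatory Biomarkers, SAP Appendix B). There it stands in the Week 12 change-from-baseline block, under the rows for mean change and percent change. Its footnote reads "Relative difference in mean score change from baseline and one-sided p-value based on the Mixed-effect Model Repeated Measure model with PROC MIXED". SAP 5.6 says of change from baseline: "A negative value reflects a decrease in a given parameter".

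SAP 8.6.2 lists the endpoint for the MMRM differently, as "Percent change in plasma biomarkers (e.g., IL-6, SAA, MMP3"). The model in SAP 5.1 is described as follows: "The repeated-measures analysis will be based on the restricted maximum likelihood method assuming an unstructured covariance structure to model the within-subject errors". Baseline is a covariate, and no transformation is mentioned. Biomarkers are exploratory secondary endpoints in SAP Table 4 and section 8.6, outside the Hochberg family of section 8.5.

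**The concern.** A ratio with a signed denominator does not carry the direction of its numerator. Levels of IL-6, SAA or MMP3 are positive, so the reading in 5.7 would be safe for levels. A mean change is not confined to positive values, and a fall in the control group is plausible in a trial that plans for 30% of control subjects to reach ACR20.

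The table could therefore show a favourable one-sided p-value beside a relative difference that the SAP's own rule labels an increase on treatment. It could also show the opposite: an apparent decrease when treatment did worse than sham. A programmer following the SAP literally would produce this without any coding error. In addition, 8.6.2 and the table footnote name different quantities, so two competent programmers could fit different models.

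**Working it through.** **The plan's own figures.** There is none for the biomarkers: the documents give no SD, distribution, expected effect or power for them. The SAP's power figures concern ACR20. Simulating 50% versus 30% with 125 per arm, one-sided 0.025 and the Stage 1 stop gives 0.774, against 0.773 stated in SAP 3.4. That confirms only the reading of sample size and alpha; 120 per arm, used below, is the stated minimum of 240 subjects.

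**Sign.** Write t and c for the mean changes on treatment and control, and R = (t − c)/c × 100. The sign of R is the sign of (t − c) times the sign of c, so it is reversed whenever c < 0.

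| t | c | t − c | R | Reading under 5.7 | Actual |
|---|---|---|---|---|---|
| −3 | −1 | −2 | (−2)/(−1) = +200% | increase | decrease |
| −30 | −10 | −20 | (−20)/(−10) = +200% | increase | decrease |
| −10 | −30 | +20 | 20/(−30) = −66.7% | decrease | increase |
| +5 | −10 | +15 | 15/(−10) = −150% | decrease | increase |
| −30 | +10 | −40 | (−40)/10 = −400% | decrease | decrease |

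**Stability.** With t = −30, c = −0.1 gives R = +29,900% and c = +0.1 gives R = −30,100%. A trivial movement in the control mean takes the estimate from one extreme to the other. The table's interval row shares the footnote and is formatted in percent, but the SAP gives no method for an interval on a ratio of two model means.

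**How likely c < 0 is.** This depends on which quantity enters the formula. Assume log-normal markers with SD σ on the log scale, baseline-to-Week-12 correlation ρ, and a 10% fall in the control geometric mean (multiplier 0.9).

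- Mean raw change (the footnote's wording). Its expectation is (0.9 − 1) × exp(σ²/2) in units of the baseline geometric mean, so it is negative for every σ. In simulations over σ 0.3 to 1.2 and ρ 0.5 to 0.7, the observed control mean was negative in 73% to 100% of trials. With no true control change it is negative in about half.
- Mean percent change (8.6.2's wording). Its expectation is 0.9 × exp[σ²(1 − ρ)] − 1. At ρ = 0.6 that is 0.9 × exp(0.036) − 1 = −6.7% for σ = 0.3, but 0.9 × exp(0.256) − 1 = +16.3% for σ = 0.8. Skew pulls the mean up while the typical marker falls. Over ρ 0.5 to 0.7, the observed mean was negative in 98% to 100% of trials at σ = 0.3, 34% to 80% at 0.5, 8% or fewer at 0.8, and about 1% or fewer from 1.0 upwards.

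**Power, conditional on shape.** Assume a true 25% reduction, 120 per arm, ρ = 0.6 and one-sided 0.025, with a baseline-adjusted comparison at Week 12 in place of the full MMRM.

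| Log SD | Percent change | Log ratio |
|---|---|---|
| 0.3 to 0.5 | about 100% | about 100% |
| 0.8 | about 82% | about 94% |
| 1.0 | about 56% | about 80% |
| 1.2 | about 37% | about 64% |

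Type I error stayed near 2.5% for both analyses.

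**The case against.** The strongest reply is about consequence. The MMRM p-value tests the difference between groups and keeps its direction. Table 14.1.2.19 prints levels, mean change and percent change for each arm directly above the relative difference, so an attentive reader can see which arm fell more. The endpoints are exploratory, with no power claim and no multiplicity-controlled inference. All of this stands. A reader might infer that the biomarker test itself, or the trial's efficacy conclusion, could be reversed; the documents do not support that.

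A second reply is that the value in 5.7 may have been meant as a marker level. On that reading nothing reverses, but the table footnote says mean change, and it is the instruction to the programmer.

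A third is that the reversal does not follow every time sham improves. On the percent-change scale of 8.6.2 this is right: with strong skew, a modest fall in the typical control marker usually leaves the mean percent change positive. A 25% sham fall, with ρ = 0.6, makes it negative in about 69% of trials at log SD 0.8 and 15% or fewer at 1.0 and above. The condition is a negative control mean of whichever quantity is used, not improvement in general.

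Finally, it is tempting to say that an untransformed analysis will lose power because these markers are skewed. The documents do not describe their distribution. The logarithm of CRP in DAS28-CRP belongs to a scoring formula and says nothing about IL-6, SAA or MMP3.

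**Conclusion.** The defect holds as a display and specification error. The sign reversal is exact and needs no distributional assumption once the footnote's quantity, mean change, is put into 5.7. The size of R is also unreliable whenever the control mean is close to zero. The mismatch between percent change and mean change is plain on the page.

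Its reach is limited to the exploratory biomarker table: the printed relative difference and any interval on that scale. The p-value, the per-arm summaries, and the primary and key secondary results are untouched.

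A log-scale analysis may also be more powerful, but only conditionally. Under the assumed log-normal shape and a 25% reduction, the gain is nil at log SD 0.3 to 0.5, where both analyses are near 100%, and about 12 to 27 points at 0.8 to 1.2. It is a reason to prefer the log scale, not a demonstrated loss. The point is minor and cheap to correct.

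**What to change.** 1. Restrict SAP 5.7 to positive levels and state that it is not used for change scores.
2. Make 5.7, 8.6.2 and the Table 14.1.2.19 footnote name the same analysed quantity. The long-term SAP needs the same check: its Table 2 names percent change at Week 24, while Table 14.8.2.17 shows change from baseline. It prints no relative difference.
3. In Table 14.1.2.19, replace the relative difference with the MMRM difference between groups and its 95% CI. Preferably, model log(post/baseline) with log baseline as covariate and report the treatment-to-control geometric mean ratio with 95% CI, where a value below 1 means lower on treatment.
4. If the log scale is used, add a rule for results below the limit of quantification. SAP 5.8.1 covers missing or unreliable values and does not say whether such results count among them.

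The cost is SAP wording, one transformation, and edits wherever percent change is named (Table 4, sections 8.6 and 8.6.2, the biomarker listings, and the long-term SAP). No new data are needed. The downside is that readers get a ratio instead of a mean percent change; the per-arm percent changes can stay as description.
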